14. SAFETY ANALYSES

All safety analyses will be performed using the actual treatment for the Safety Analysis Set.

14.1 Adverse Events

The primary endpoint for this study is treatment-emergent adverse events (TEAEs). Adverse events will be coded using MedDRA dictionary, Version 23.0.

An AE (classified by preferred term) will be considered a treatment-emergent AE (TEAE) if started after first study dose administration and no later than last study dose date + 30. AEs reported on Day 1 based on Baseline (pre-dose) findings (e.g., clinically significantly abnormal vital signs, laboratory test results, or electrocardiogram parameters) will not be considered as TEAEs.

The number and percentage of subjects reporting TEAEs in each treatment group will be tabulated by system organ class (SOC) and preferred term; by SOC, preferred term, and maximum severity; and by SOC, preferred term, and relationship to study drug. If more than 1 AE occurs with the same preferred term for the same subject, then the subject will be counted only once for that preferred term using the most severe and most related occurrence for the summarization by severity and by relationship to study drug.

The relationship of selected AEs to COVID-19 will be assessed as detailed in the GSD. COVID-19 related adverse events will be listed separately.

TEAEs will also be tabulated by treatment group and without displaying the SOC terms; this table will be sorted in descending order of frequency of preferred term within the pimavanserin group.

The incidence of most frequently reported (preferred terms reported by 2 or more subjects) TEAEs, treatment emergent SAEs, and TEAEs leading to discontinuation of study drug will be summarized by SOC, preferred term, and treatment group. The tables will be sorted alphabetically by SOC and then by descending frequency within each SOC. In addition, the incidence of fatal treatment-emergent AEs (i.e., events that cause death) will be summarized separately by preferred term and treatment group.

An AE listing by subject will display all events, including those which occur during screening, and will include the verbatim term in addition to the MedDRA SOC and preferred term. This listing will also include all relevant eCRF data associated with the event: date of onset, date resolved, date of last dose, severity, frequency, outcome, relationship to study drug, and action taken with study drug. Separate listings will be presented for subjects with treatment-emergent SAEs, subjects with TEAEs leading to discontinuation, subject who died (if any), and COVID-19 related adverse events.

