3.1.2 Double-blind Treatment Period (4 Weeks)

The Baseline visit (Visit 2) may occur after screening procedures are completed, subject eligibility has been confirmed, and no earlier than 7 days after the subject has been given the wearable device. At the Baseline visit (Visit 2), eligible subjects will be randomized in a 1:1:1 ratio to pimavanserin 34 mg, quetiapine 25 mg, or matching placebo.

Subjects who are randomized to the quetiapine treatment group will begin dosing at 25 mg. At Week 1 (Visit 3), Week 2 (Visit 4) and Week 3 (Visit 5), the Investigator will be encouraged to increase the dose of blinded study drug, consistent with 50-100 mg quetiapine, based on the Investigator's assessment of clinical response ([Figure S-2](#)). Dose adjustments will be implemented through interactive response technology (IRT) system. In actuality, only the dose of quetiapine would be increased (to 50 mg at Week 1 and then optionally to 100 mg at Week 2 or Week 3); the pimavanserin dose will remain fixed at 34 mg per day throughout the study. The Investigator will be blinded to study drug and thus will not know whether their decision to increase the dose of blinded study drug results in an actual increase in study drug

dose. The dose of study drug (pimavanserin, quetiapine or placebo) may not be decreased. If a subject cannot tolerate their dose, they must be withdrawn from the study.

Subjects for whom the Investigator does not increase the dose of blinded study drug consistent with 50 mg quetiapine at Week 1 (Visit 3) will be withdrawn from the study and replaced. A maximum of 12 subjects across treatment groups (20%) will be replaced for this and only this reason.

Assessments in the clinic will be conducted at Weeks 0 (Baseline), 1, 2, 3, and 4/end of treatment (EOT). Assessments on the handheld device will be collected from Baseline to Week 4/EOT on a regular basis (see [Table S-2](#)).

Subjects will be provided standard of care treatment per investigator judgment for 3 months following their completion of the double-blind treatment period.

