4.6.1 Permitted, Restricted, and Prohibited Medications

Prohibitions and restrictions for concomitant medications should be followed between the initial screening visit and Week 4/Visit 6/ET as specified in [Appendix A](#) and [Appendix B](#). These appendices do not constitute an exhaustive list and any questions regarding prohibited and restricted medications should be discussed with the Medical Monitor or designee.

Use of medications that could interfere with study conduct or any questions regarding prohibited and restricted concomitant medications should be reviewed and/or discussed with the Medical Monitor or designee.

Medications that can prolong QT interval are prohibited (or restricted if approved by the Medical Monitor) as specified in [Appendix A](#).

Permitted concomitant medications should remain at a stable dose throughout the study.

If a subject is on a medication restricted by the protocol, the medication should be adjusted if it is determined by the Investigator to be clinically appropriate (e.g., if the subjects symptoms are not well-controlled or if the subject cannot tolerate the current medication) in consultation with the treating physician.

Subjects who require current treatment with a prohibited medication will be withdrawn from the study.

Subjects who have previously taken a prohibited medication during the study will be withdrawn from the study unless:

- the prohibited medication has been discontinued AND
- withdrawal from the study presents an unacceptable medical risk to the subject

The justification to allow the subject to continue in the trial will be made by the Sponsor/Medical Monitor, with medical input from the Investigator, and will be documented. If a subject is allowed to remain in the trial, this will be reported as a major protocol deviation and not a waiver.

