5.1.3 Dosing and Administration

Bottles of study drug will be dispensed to the subject at Baseline and at Weeks 1, 2 and 3. Each daily dose consists of two individual capsules that should be taken together. Subjects will begin dosing at the Baseline visit after eligibility is confirmed. At Baseline and at each subsequent clinic visit, subjects will be dosed and will remain in the clinic for observation for a minimum of 60 minutes after dosing. Subjects should not take study drug on the mornings of clinic visit days until instructed to do so by the site staff.

Subjects are to take two whole capsules, orally, once daily in the morning (prior to the subject's daily assessments). Investigators/study staff and subjects should be instructed to not open the capsules. The capsules may be taken with or without food.

Subjects who are randomized to the quetiapine treatment group will begin dosing at 25 mg. At Week 1 (Visit 3), Week 2 (Visit 4) and Week 3 (Visit 5), the Investigator will be encouraged to increase the dose of blinded study drug, consistent with 50-100 mg quetiapine, based on the Investigator's assessment of clinical response ([Figure S-2](#)). Dose adjustments will be implemented through the IRT. In actuality, only the dose of quetiapine would be increased (to 50 mg at Week 1 and then optionally to 100 mg at Week 2 or Week 3); the pimavanserin dose will remain fixed at 34 mg per day throughout the study ([Figure S-2](#)).

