6.4 Safety Follow-up

A 30-day safety follow-up telephone contact is to be completed for subjects who complete the treatment period of the study as well as those who discontinue prematurely from the study. Subjects should have the following completed 30 (± 4) days after last dose of study drug:

- Assessment of concomitant medications/treatments
- Assessment of AEs

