9.5 Statistical Analyses

9.5.1 Primary Analyses

Adverse events will be classified into standard terminology using the Medical Dictionary for Regulatory Activities. All AEs will be listed and TEAEs will be summarized by system organ class and preferred term.

A TEAE is defined as an AE that occurs after the first dose of study drug and up to 30 days after the last dose of study drug. Summaries by maximum severity and by relationship will also be provided. Serious TEAEs, fatal AEs, and TEAEs leading to discontinuation will also be summarized.

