Serotonin antagonists	PROHIBITED 
 • ciproheptadine 	
 • Prohibited throughout the study until completion of the EOT visit • Must be discontinued at least 3 weeks prior to the Baseline visit
Antiarrhythmic drugs	PROHIBITED 
 • ajmaline • amakalant, semantilide • amiodarone • bretylium • disopyramide • dofetilide • dronedarone • flecainide • ibutilide • procainamide • propafenone • quinidine • sotalol, d-sotalol 	Prohibited at Baseline and throughout the study until completion of the EOT visit
Opioids	PROHIBITED 
 • methadone 	Prohibited at Baseline and throughout the study until completion of the EOT visit
Antimicrobials, antifungals, and antimalarials	PROHIBITED 
 • clarithromycin • erythromycin • levofloxacin • moxifloxacin • pentamidine • roxithromycin 	Prohibited at Baseline and throughout the study until completion of the EOT visit
	RESTRICTED 
 • artenimol/piperaquine • azithromycin 	
 • Prohibited at Baseline but may be used during the course of the study to treat a bacterial infection (e.g., urinary tract infection, respiratory infection), post-Baseline at the discretion of the Principal Investigator.

Medication Class	Medication ^a	Prohibition/restrictions
	
• bedaquiline• ciprofloxacin• gemifloxacin• norfloxacin• ofloxacin• fluconazole• telavancin• telithromycin	
• The medications on the left are only allowed under the following conditions:
○ The subject has a Baseline ECG with a QTcF <425 ms IF QRS duration is <120 ms OR○ The subject has a QTcF <450 ms at Baseline IF QRS duration \geq120 ms

^a Medications within each class include but are not limited to the examples listed in this table.

Appendix B Prohibited and Restricted Concomitant Medications: Inhibitors and Inducers of Cytochrome P450 Enzyme 3A4

The information presented here is intended to provide guidance and does not constitute an exhaustive list of strong CYP 3A4 enzyme (CYP3A4) inhibitors and inducers. Any questions should be discussed with the Medical Monitor or appropriate designee. Details regarding procedures for subjects who take a prohibited or restricted medication during the study are provided in [Section 4.6.1](#).

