1. INTRODUCTION

This statistical analysis plan (SAP) provides a technical and detailed elaboration of the statistical analyses of efficacy and safety data as described in Protocol Amendment 3, dated 31 January 2020. Specifications for tables, figures, and listings are contained in a separate document. Actigraphy and Ecological Momentary Analysis (EMA) data collected on the Handheld Device will be analyzed as described in a separate, stand-alone SAP.

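### Does counting adverse events up to 30 days after the last dose, with no split at the last dose, undermine the primary safety summary?

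*SAP*

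**What the plan says.** SAP section 14.1 counts an adverse event as treatment-emergent "if started after first study dose administration and no later than last study dose date + 30". Protocol section 9.5.1 gives the same rule: an event that "occurs after the first dose of study drug and up to 30 days after the last dose of study drug". The two documents agree.

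SAP 14.1 then describes these TEAE tables by arm:

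- by system organ class and preferred term
- the same by maximum severity, and by relationship to study drug
- by preferred term alone
- preferred terms reported by 2 or more subjects
- serious events
- events leading to discontinuation of study drug
- fatal events

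None is divided at the last dose. The by-subject listing in the same section shows, for every event, the onset and resolution dates, last-dose date, severity, relationship and action taken. SAP section 11 separates medications at the last dose and summarizes post-treatment medications by study drug. On table layouts, SAP section 1 says: "Specifications for tables, figures, and listings are contained in a separate document". That document was not available for this review.

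**The concern.** Conditions change at the last dose. Protocol section 4.6.1 says "Prohibitions and restrictions for concomitant medications should be followed between the initial screening visit and Week 4/Visit 6/ET", and the antipsychotics row of Appendix A reads "Prohibited throughout the study until completion of the EOT visit". Protocol section 3.1.2 adds: "Subjects will be provided standard of care treatment per investigator judgment for 3 months following their completion of the double-blind treatment period". Enrolled subjects have symptoms judged to warrant an antipsychotic, so a placebo subject could start one within the 30-day tail. A resulting event would be counted as a placebo TEAE.

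Follow-up also thins out. There are four scheduled clinic visits after Baseline on treatment, then one call: "A 30-day safety follow-up telephone contact is to be completed for subjects who complete the treatment period of the study". The severity and relationship tables take the worst occurrence per preferred term across the whole window, so a mild event on drug and a severe one afterwards merge into one severe TEAE.

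The primary objective is safety and tolerability compared with placebo. If about half the window is not on treatment, the pooled percentages might not show what happened on drug.

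**Working it through.** **Reproducing the plan's figure.** Treatment lasts 28 days and follow-up is 30 days: 28 + 30 = 58, the Day 58 of the schedule (protocol Table S-1, SAP Table 6). SAP Table 1 numbers the first dose as study day 1, so its target is 58 + 1 = 59. Both agree with the TEAE window.

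**Share of the window after the last dose.** Share = 30 / (days on treatment + 30). Protocol section 5.1.3 says "At Baseline and at each subsequent clinic visit, subjects will be dosed", so the last dose may fall on the Week 4 visit, giving 28 to 29 days on treatment.

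| Case | Days on treatment | Share after last dose |
|---|---|---|
| Completer | 28-29 | 30/58 = 51.7%; 30/59 = 50.8% |
| Completer, visit window ±3 days | 25-32 | 30/55 = 54.5%; 30/62 = 48.4% |
| Withdrawn at Week 1 | 7-8 | 30/37 = 81.1%; 30/38 = 78.9% |
| Withdrawn at Week 1, ±3 days | 4-11 | 30/34 = 88.2%; 30/41 = 73.2% |

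If the call comes on the earliest permitted day (last dose + 26), a completer's share of covered time is 26/54 = 48.1% or 26/55 = 47.3%.

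**Person-time.** SAP section 19 reports 11 randomized subjects. If all completed (an assumption; completers are not given), time on treatment is 11 × 28 = 308 to 11 × 29 = 319 person-days, against 11 × 30 = 330 afterwards.

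**What these figures can show.** They are shares of calendar time. The share of TEAEs arising in the tail cannot be derived from them, because events are sought at four clinic visits in one period and by one call in the other. Neither document gives event rates by period. The size and direction of any distortion are therefore unknown. The tail is defined identically in all three arms.

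**What the reader will already have.**

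1. Onset and last-dose dates stand together in the adverse event listing, so each event can be placed before or after the last dose. With 11 subjects this is a short hand count.
2. New medication after the last dose is tabulated by study drug under SAP 11. SAP section 5 lists all collected data except actigraphy and handheld data, so a drug's start date can be set against an event's onset date.
3. The table of TEAEs leading to discontinuation mainly captures events that arose while dosing continued, and it bears directly on tolerability. It is not the missing split, but it narrows what the split would add.

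**What a split would resolve.** Arm sizes are not given. At an assumed 3 to 4 subjects per arm, one subject is 1/4 = 25 to 1/3 = 33 percentage points. Dividing such counts by period makes them sparser. No hypothesis test is planned for TEAEs, since protocol section 9.2 confines testing to exploratory endpoints.

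**The case for a change.** The strongest argument for the concern is that the boundary matters clinically and the SAP already uses it. Section 11 divides medications at the last dose and section 5.4 imputes missing last-dose dates. Carrying that boundary into the primary endpoint would need no new data, and a written rule is better than each reader dividing the listing in their own way. With so few subjects per arm, one post-treatment event can also move a percentage a long way. Subjects withdrawn at Week 1 because the dose was not increased remain in the Safety Analysis Set, so the table can mix very different times on treatment.

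The facts stand: the window, the arithmetic, and the absence of a split in any described table. A period table would be reasonable to add. Three things keep this from being a deficiency.

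First, no effect on the result is shown. The route through newly started antipsychotics is possible but not documented: the protocol says only that standard of care is provided. Nor do the documents say that any of the 11 subjects withdrew at Week 1.

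Second, the split would not isolate drug effect, because delayed or residual effects would fall in the later period. It would also need rules of its own. Protocol section 7.2.2.1 closes an event record when severity changes in either direction, so an event that eases after the last dose might be recorded again and look new. Drugs begun on the last-dose date count as concomitant under SAP 11, so any medication flag would need a boundary consistent with that.

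Third, the absence is not established, because the table specifications were not available and may contain the split.

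**Conclusion.** The concern does not hold. The plan defines one TEAE window, states it identically in protocol and SAP, and applies it equally to every arm. Followed as written, it gives a sound descriptive summary that also captures late safety events.

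About half of a completer's window (51-52%; 48-55% across visit windows) follows the last dose, but this is a share of time with no demonstrated effect on any result. The on-treatment picture can be recovered from the planned listing. A split table would change no definition, test or conclusion.

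This rests on the 11 randomized subjects reported in SAP 19 and on the listing being produced as described. The person-days assume that all 11 completed, and the 25 to 33 points per subject assume 3 to 4 per arm. The judgement depends on neither assumption.

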14.2 Clinical Laboratory Variables

Due to COVID-19 disruptions it is possible that some test results may be collected from a local laboratory. Local laboratory results will not be included in any data analysis. Local laboratory results (if collected) will be included in data listings.

Clinical laboratory assessments are performed at Screening Visit 1, Baseline (Week 0), Visit 4 (Week 2), and Visit 6 (Week 4/EOT/ET).

- Clinical chemistry serum tests include the following:
 - Sodium (Na), potassium (K), chloride (Cl), phosphorus (P), calcium (Ca), magnesium (Mg), carbon dioxide (CO₂), blood urea nitrogen (BUN), creatinine (CR), uric acid
 - Mg is only performed at Visit 1 (Screening)
 - Alanine aminotransferase (ALT), aspartate aminotransferase (AST), gamma-glutamyl transpeptidase (GGT), alkaline phosphatase (ALP), total bilirubin (TBIL), lactate dehydrogenase (LDH)
 - Vitamin B12 (Screening only)
 - HbA1c (Screening only)
 - Glucose
 - Albumin (ALB), total protein
 - Prolactin (Week 4/EOT will be blinded, also performed at Baseline)
 - Thyroid stimulating hormone (TSH) and reflex free T4, if TSH is out of range
 - TSH/free T4 is only performed at Visit 1 (Screening)
 - Creatine kinase (CK)/creatine phosphokinase (CPK)
 - Insulin (at Baseline and Week 4 only)
 - Lipid panel
 - Total cholesterol, HDL-cholesterol, triglycerides, LDL-cholesterol, Cholesterol/HDL ratio, Non-HDL cholesterol, very low density lipoprotein cholesterol
- Hematology tests include the following:
 - Complete blood count (CBC) including:

- White blood cell (WBC) count
- Absolute neutrophil count
- Complete differential (relative and absolute)
- Hematocrit (Hct), hemoglobin, red blood cells (RBC), platelets
- Reticulocyte count
- Urinalysis tests include the following:
 - Blood, RBCs, WBCs, protein, glucose, ketones, specific gravity, pH

Clinical laboratory values (in Système International [SI] units) and the change from Baseline values will be summarized by treatment group at Weeks 2 and 4(EOT/ET) using descriptive statistics. The overall minimum, maximum and last post-Baseline observed and change from Baseline values will also be summarized. For hemoglobin, hematocrit and uric acid, the above summaries will be presented for each gender as well as for both genders combined. For urinalysis with categorical results, the number and percentage of subjects will be tabulated by category at Baseline, Weeks 2 and 4 (EOT/ET); and the denominator is the number of subjects with non-missing values for the given parameter, visit and treatment group.

Laboratory values will also be summarized in shift tables by treatment group, to determine the number and percentage of subjects with values classified as below, within, and above normal ranges at Weeks 2 and 4 (EOT/ET) relative to the same classification at the Baseline visit. For the by-visit shift summary, the denominator is the number of subjects with non-missing values at Baseline and the given visit for the given parameter and treatment group. For the shift to the overall post-Baseline minimum or maximum, all post-Baseline values will be considered, including unscheduled and out of window values and the denominator is the number of subjects with non-missing Baseline value and at least 1 post-Baseline value for the given parameter and treatment group. For hemoglobin, hematocrit and uric acid, the shift summaries will be presented for each gender as well as for both genders combined.

Clinical laboratory values are potentially clinically important (PCI) if they meet either the low or high PCI criteria listed in [Tables 2](#) and [3](#). The number and percentage of subjects with post-Baseline PCI values for each of the categories in [Table 7](#) and [8](#) will be summarized by treatment group for selected parameters. For the overall post-Baseline summaries of PCI values, all post-Baseline values will be considered, including unscheduled and out of window values. Subjects with multiple PCI values for a given parameter will be counted only once for that parameter. For the overall post-Baseline summary, the numerator of the percentage is the number of subjects with at least 1 post-Baseline PCI laboratory value for the given parameter and treatment group,

and the denominator is the number of subjects with at least 1 post-Baseline laboratory value for the given parameter and treatment group. For hemoglobin, hematocrit and uric acid, the count and percentage of subjects with PCI values will be presented for each gender as well as for both genders combined. Subjects with PCI values will be presented in an additional listing.

Table 2 Criteria for Potentially Clinically Important Laboratory Values – Hematology and Chemistry

Analyte	Conventional Unit	Low PCI Criteria	High PCI Criteria	SI Unit	Low PCI Criteria	High PCI Criteria
Hematology (whole blood)						
Hemoglobin (male)	g/dL	<11	>18	g/L	<110	>180
Hemoglobin (female)	g/dL	<10	>17	g/L	<100	>170
Hematocrit (male)	%	<30	>55	L/L	<0.3	>0.55
Hematocrit (female)	%	<30	>50	L/L	<0.3	>0.5
Leukocyte (White Blood Cell Count)	$\times 10^3/\mu\text{L}$	≤ 2.8	≥ 15	$\times 10^9/\text{L}$	≤ 2.8	≥ 15
Neutrophils	$\times 10^3/\mu\text{L}$	≤ 1.5	No upper limit	$\times 10^9/\text{L}$	≤ 1.5	No upper limit
Platelet Count	$\times 10^3/\mu\text{L}$	≤ 75	≥ 700	$10^9/\text{L}$	≤ 75	≥ 700
Chemistry (serum or plasma)						
ALT (SGPT)	U/L	No lower limit	$\geq 3 \times \text{ULN}$	U/L	No lower limit	$\geq 3 \times \text{ULN}$
AST (SGOT)	U/L	No lower limit	$\geq 3 \times \text{ULN}$	U/L	No lower limit	$\geq 3 \times \text{ULN}$
Total Bilirubin	mg/dL	No lower limit	$\geq 1.5 \text{ ULN}$	umol/L	No lower limit	$\geq 1.5 \text{ ULN}$
BUN	mg/dL	No lower limit	≥ 30.0	mmol/L	No lower limit	≥ 10.71
Creatine Kinase (CK)	U/L	No lower limit	$\geq 3 \text{ ULN}$	U/L	No lower limit	$\geq 3 \text{ ULN}$
Sodium	mEq/L	≤ 125	≥ 155	mmol/L	≤ 125	≥ 155
Potassium	mEq/L	≤ 3.0	≥ 5.5	mmol/L	≤ 3.0	≥ 5.5
Calcium, total	mg/dL	<8.0	>11.0	mmol/L	<2.0	>2.75
Lactate Dehydrogenase (LDH)	U/L	No lower limit	$\geq 3 \times \text{ULN}$	U/L	No lower limit	$\geq 3 \times \text{ULN}$
Alkaline Phosphatase	U/L	No lower limit	$\geq 3 \times \text{ULN}$	U/L	No lower limit	$\geq 3 \times \text{ULN}$

Table 2 Criteria for Potentially Clinically Important Laboratory Values – Hematology and Chemistry (Continued)

Analyte	Conventional Unit	Low PCI Criteria	High PCI Criteria	SI Unit	Low PCI Criteria	High PCI Criteria
Uric acid (male)	mg/dL	No lower limit	≥ 10.5	umol/L	No lower limit	≥ 624.75
Uric acid (female)	mg/dL	No lower limit	≥ 8.5	umol/L	No lower limit	≥ 505.75
Albumin	g/dL	≤ 2.6	≥ 6.0	g/L	≤ 26	≥ 60
Total Protein	g/dL	≤ 5.0	≥ 10.0	g/L	≤ 50	≥ 100
Chloride	mEq/L	≤ 85	≥ 120	mmol/L	≤ 85	≥ 120
Glucose (random)	mg/dL	≤ 45.1	≥ 200.0	mmol/L	≤ 2.48	≥ 11
Serum Creatinine	mg/dL	Not Applicable	>1.5 ULN	umol/L	Not Applicable	>1.5 ULN
Triglycerides	mg/dL	Not Applicable	>300	mmol/L	Not Applicable	>3.39
Gamma-Glutamyl Transferase (GGT)	U/L	Not Applicable	≥ 3 ULN	U/L	Not Applicable	≥ 3 ULN

Table 3 Criteria for Potentially Clinically Important Laboratory Values – Urinalysis

Urinalysis (qualitative dipstick)	Low PCI Criteria	High PCI Criteria
Blood (occult blood)	Not Applicable	\geq Moderate
Protein	Not Applicable	≥ 100 mg/dL
Glucose	Not Applicable	≥ 500 mg/dL

Clinical laboratory data will be displayed in data listings with date and study day of collection. All units will be displayed according to SI conventions for units. Out of range values will be flagged in the data listings (i.e., 'L' or 'H'). A separate listing will be provided for a subset of the chemistry, hematology, and urinalysis analytes with values classified as PCI.

The pregnancy results (positive or negative) for female subjects will be presented in a listing.

